## Rationale

Immediate postpartum initiation of the etonogestrel contraceptive implant has been proven to decrease rates of rapid, repeat pregnancies. Evidence supports that in healthy women with term infants initiation of the contraceptive implant 1-3 days postpartum does not appear to have any adverse effects on lactogenesis or breastfeeding continuation. However, no high quality study to date has examined the effects of progestin-only contraception in women known to be at risk for low milk supply, including women with a premature delivery, obesity, polycystic ovarian syndrome, diabetes, or a prior history of low milk supply. Preventing unintended pregnancy in this population of women is particularly important, as many of the conditions that put women at risk for difficulty with breastfeeding also increase the likelihood of a medically complex pregnancy with poorer outcomes for both women and infants. Clinicians, hospital systems, and policy makers working to expand access to immediate postpartum implants and desiring to support women in meeting their breastfeeding goals need quality evidence to guide them when offering immediate postpartum implants to some of their most medically complex patients.

It is unclear if the specific timing of immediate postpartum implant initiation may have an effect on breastfeeding success. Theoretically, exposure to progesterone prior to the establishment of lactogenesis may interfere with the successful establishment of a milk supply. In creating work flows to increase access to postpartum implants, placing an implant within 30 minutes of delivery may be the most efficient and streamlined option for many settings. However, no data exists on the effect of initiating a contraceptive implant prior to 1-3 days postpartum on the timing of lactogenesis or breastfeeding duration.

## **Research Design and Methods**

### *Research Design and Study Subjects*

This will be a three-armed randomized non-inferiority study of women delivering at the Weiler Hospital of the Albert Einstein College of Medicine who plan to breastfeed, have known risk factors for low milk supply, and who intend to use the contraceptive implant postpartum. Women will be randomized to one of three groups: device placed within 30 minutes of placental delivery, 24-72 hours postpartum, or 6 or more weeks postpartum. All study activities will adhere to the CONSORT guidelines for reporting randomized trials. Women will be assessed at enrollment, 1-5 days postpartum, 6 weeks, 3 months and 6 months postpartum.

Eligibility Criteria will include:

- 1) Live pregnancy of at least 24 weeks gestation
- 2) Intention to use a contraceptive implant postpartum
- 3) Intention to use a non-hormonal bridging method of contraception until a contraceptive implant can be placed
- 4) 18 years of age or older
- 5) English or Spanish speaking
- 6) Women will be enrolled either during prenatal care or upon admission to Labor and Delivery.
- 7) Absence of pain. Among women who are being enrolled on Labor and Delivery MUST fall into one of the three following categories:

- Women presenting for induction of labor. Women will be approached and enrolled prior to the onset of labor.
- Women presenting for a planned cesarean delivery. Women will be approached and enrolled prior to entry into the operating room.

- Women who have an Epidural in place for management of pain. Prior to engaging in a discussion regarding the study protocol, women will be asked if they are experiencing any pain, and if the answer is yes, they will not be eligible for entry into the study.

7) Presence of at least one of the following conditions known to be a risk factor for low milk supply:

- Expected delivery prior to 37 weeks
- Obesity (pre-pregnancy BMI >35)
- Polycystic Ovarian Syndrome
- Diabetes (gestational or pre-gestational)
- Self-reported difficulty with low milk supply in past

*Setting and Population*

Efforts will be made to identify and recruit eligible women during their prenatal at outpatient Montefiore Health Centers affiliated with the Weiler Hospital of the Albert Einstein College of Medicine in the Bronx, NY. The Bronx is home to the poorest congressional district in the country, and the worst healthcare outcomes in New York State. One in three adults in the Bronx is obese, and in the poorer neighborhoods a full 61% are either obese, diabetic, or both. In 2013, there were 4023 deliveries at Weiler Hospital, most to poor women of color (Table 1).

Table 1: Demographics of women delivering at Weiler Hospital in 2013

Age		Race		Ethnicity		Insurance Type	
<20	7.1%	Black or African American	31.3%	Hispanic or Latina	48.9%	Medicaid and Self-Pay	64.7%
20-30	57.7%	White	11.0%	Non-Hispanic or Latina	45.9%	Private Insurance	35.3%
>30		Asian	3.4%	Declined	5.2%	Socioeconomic Status	
		Multiracial	41.5%			Below NYS Average	91.2%
		Declined	12.8%			Above NYS Average	8.8%

Since July of 2014 immediate postpartum initiation of LARC devices has been available to all medically eligible women at Weiler Hospital. Currently we place approximately 100

devices, including 60 implants each month. As the tertiary referral center in a vulnerable and high-risk community, it is reasonable to estimate that at least 50% of the women who deliver at Weiler Hospital have at least one risk factor for low milk supply.

### *Recruitment*

For women who receive prenatal care within the Montefiore system, the recruitment process will start during their prenatal visits. It is a routine part of prenatal care for women to get contraceptive counseling and education about the benefits of breastfeeding. Flyers and brochures advertising the study will be made available to all clinical sites providing prenatal care and to all prenatal care providers. Women will have the opportunity to review these materials, contact the research team with any questions, and review the consent form prior to admission to labor and delivery if they desire.

Women who are interested in enrolling in the study will be identified by prenatal care providers and research study staff will call the women and provide information about the study. Women will have the opportunity to consent for participation into the study over the phone. In these cases, a pop-up message will be created in EPIC to alert the study team when this patient present for admission to Labor and Delivery. Once these women present to Labor and Delivery they will also be asked to sign a study consent form and reaffirm their desire to participate in the study. They will be randomized into the trial only once they present to Labor and Delivery and reaffirm their desire to participate in the trial.

It is standard practice at Montefiore to counsel all women on admission to Labor and Delivery about their contraceptive options, including immediate postpartum IUDs and implants upon admission. This counseling is provided by the admitting resident, PA or faculty on Labor and Delivery. The admitting team routinely reviews and documents a contraceptive plan and breastfeeding intentions for each woman admitted to labor and delivery. The study's research coordinators will review the patients admitted to Labor and Delivery regularly (1-3 times daily) in order to identify women eligible for participation in this trial. Only those women who have a documented intention to use a contraceptive implant postpartum will be approached by the study team for possible enrollment into the trial.

Women will be enrolled, consented and randomized on Labor and Delivery, prior to delivery. The study brochure will be included in the standard educational materials provided to all women on admission to Labor and Delivery. All enrollment and screening will be done in private labor and delivery rooms and all measures will be taken to ensure patient privacy. Women will be explicitly told that their participation in this trial is voluntary and that they have the option of receiving a contraceptive implant at any of the time points included in this study if they decline participation in this trial. Only co-investigators who have completed CITI training and who are intimately familiar with the study protocol will be approaching or enrolling patients into the trial.

During the informed consent process, women will receive standardized contraceptive counseling, including information about the contraceptive implant and its potential effects on breastfeeding. Women who are eligible for the trial and interested in participating will be enrolled and randomized in a 1:1:1 ratio to one of the three groups to determine their timing of contraceptive implant placement. Participants will be assigned using computer-generated random numbers in blocks of varying sizes with strict allocation concealment using sequentially numbered opaque envelopes. Women will be informed of their randomization group at the time of enrollment into the trial.

Women randomized to receive the implant within 30 minutes of delivery will have the implant placed in the delivery room or operating room within 30 minutes of placental delivery. Placement of the implant will not interfere with any skin-to-skin interactions that are currently routinely encouraged for the mother and infant after every delivery. Women randomized to receive the implant within 1-3 days of delivery will have their implant placed on the postpartum unit more than 24 hours after delivery, but prior to discharge from the hospital. Women randomized to receive the implant at 6 or more weeks postpartum will be scheduled for an outpatient visit with the family planning clinic at 6-8 weeks postpartum for implant placement.

#### *Study Procedures*

Follow-up and data collection for participants in all three groups will be identical. In order to achieve specific aim 1, time to lactogenesis stage II will be measured based on maternal perception based on measures described and validated by Chapman et al and utilized in a similar study by Gurtcheff et al. Beginning on the first postpartum day,

subjects will be contacted daily. Subjects will be asked, "Has your milk come in? Some women experience this as a prickly feeling or tingling in the breast, dripping from the other nipple when nursing, milk running from the baby's mouth, or gulping by the baby." If the response is positive, women will then be asked, "When did your milk come in?" and the response recorded to the nearest hour. If lactogenesis has not occurred prior to hospital discharge, the patient will be contacted at least daily by their preferred method (phone, text or email) from study personnel until lactogenesis can be confirmed and recorded.

To achieve specific aim 2, women will complete study follow-up questionnaires at 6 weeks, 3 months and 6 months postpartum either by phone interview or by electronic web-survey, depending on the participant's preference. These questionnaires will assess breastfeeding status, exclusivity and satisfaction as well as contraceptive method continuation, satisfaction, and side effects, including bleeding. Women will be asked to contact the study coordinators when they stop breastfeeding or if they discontinue the contraceptive implant.

*Recruitment, Follow-up and Retention.*

Successful recruitment, follow-up and retention represents the most significant challenge to the completion of this project. The population of women we intend to enroll is socioeconomically disadvantaged and has high rates of non-adherence to postpartum care. Only 43% of women who deliver at Weiler attend a postpartum visit within 12 weeks of delivery. While this is a difficult to study population, they are also the women who may benefit the most from access to immediate postpartum contraception as attendance at a postpartum visit clearly represents a significant barrier to care for most of these women. [name] has a proven track record of successfully following women in this specific community in the immediate postpartum period. She served as the principal investigator on a set of trials examining the effects of a primary care intervention on breastfeeding outcomes. During these trials she successfully recruited and followed a cohort of postpartum women from our institution and has developed a set of proven strategies for ensuring high levels of retention among a population of women with historically high attrition rates. We intend to use the following specific strategies:

- 1) Strong Rapport with the Participants

- a) Research Coordinators (RC) will visit the women enrolled in to the study at least twice during their postpartum admission to encourage rapport building
- b) RCs will maintain regular contact with participants throughout the follow up period via text and email. Reminders will be emailed and texted in the weeks prior to any scheduled follow-up.
- c) RCs will send birthday ECards for all the study participants.
- d) Participants will be provided with business cards and other items (pens, magnets) containing the RC cell phone number and study contact information.

2) Convenience for the Participants

- a) Brief- Upon final pilot testing the follow-up questionnaires will take < 15 minutes to complete.
- b) Flexible methods- Participants will have the option of completing the follow-up questionnaires via phone or web survey.
- c) Flexible hours- Women will indicate their preferred times to be called, including nights and weekends
- d) Bilingual- All written study materials will be available in both English and Spanish. The RCs will be bilingual.

3) Educational and Appropriate Materials and Questionnaires

- a) The interview scripts and questionnaires will be developed to utilize non-judgmental language. The scripts and questionnaires will be piloted for content, clarity, and appropriateness prior to beginning enrollment.
- b) Educational materials regarding contraceptive options and breastfeeding support will be made available to all women participating in the cohort. Study personnel will be available to answers women's questions regarding their breastfeeding and contraceptive options.

4) Strategies for Maximizing Retention

- a) Multiple Contacts- Upon enrollment, we will obtain all potential contact options for the woman that she is willing to share (cell and home phone numbers, home address, and email), as well as contact information for at least three other people.
- b) Research Coordinators will send out texts, emails and postcards to alert participants if they were unable to be reached for an interview.

5) Patient Incentives

a) Women will be given \$50 at enrollment and \$30 for completion of each subsequent follow-up questionnaire. Incentives will be disbursed using debit cards that allow money to be transferred electronically, allowing the women to have access to the money within 24 hours of survey completion. This dollar amount is in line with other projects that have had >90% retention over one year in our Bronx population.

#### *Sample Size*

To achieve specific aim 1, we chose a non-inferiority margin of an additional 8 hours to achieve lactogenesis II, as this would be clinically relevant. In order to achieve 80% power, using a one-sided Type 1 error of 5%, and with a standard deviation in time to lactogenesis of up to 18 hours, 63 women would be needed in each group, for a total of 189 women.

To achieve specific aim 2, larger sample size will be required. Prior studies in our population have found that breastfeeding continuation rates at 6 months postpartum are 27%. Assuming a non-inferiority margin of 15%, to achieve 80% power using a one-sided Type 1 error of 5%, we would need to enroll 109 women per group, for a total of 327 women total. Assuming a 15% loss to follow up rate, we will enroll 375 women total, 125 in each group. This recruitment goal will be met over an 18 month time period and is attainable based on the approximately 60 implants placed each month on the Labor and Delivery and Postpartum units.

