#### Frequency

Enrollment will be complete when 375 subjects are enrolled into the trial. Approximately 25 subjects will be enrolled per month. The research team will review the study database and cross check to the medical record for accuracy. Quality assurance will be conducted periodically throughout the study as described below:

- The first time-point of review will occur after the first 5 subjects have been enrolled.
- If no issues of concern are noted, subsequent quality monitoring will occur at least every 6 months by 2 persons on the research team. All findings will be discussed with primary investigator and any concerns will be shared with members of the safety monitoring board.
- The final point of review will be conducted when 100% of the subjects have been enrolled and completed the study.

Additional quality data check may occur on an as-needed basis as determined by the principal investigator.

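### At the protocol's own 15% loss, 125 women per group leave about 106 evaluable, not the 109 that aim 2 is said to need; power is about 79%, not 80%

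*Combined protocol and SAP*

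**What the plan says.** All the sample size figures are in the Sample Size section of the combined protocol and SAP.

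- **Aim 1** (time to lactogenesis II): margin 8 hours, standard deviation up to 18 hours, one-sided 5%, 80% power. Result: "63 women would be needed in each group, for a total of 189 women".
- **Aim 2** (breastfeeding continuation at 6 months): expected rate 27%, margin 15%, same error rate and power. Result: "we would need to enroll 109 women per group, for a total of 327 women total". This is the larger requirement, so it sets the trial's size.
- **Loss allowance**, in the next sentence: "Assuming a 15% loss to follow up rate, we will enroll 375 women total, 125 in each group".

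The Frequency section, under Data Quality, uses the same total as the end of recruitment: "Enrollment will be complete when 375 subjects are enrolled into the trial". The Recruitment section makes the groups equal in size, with women "enrolled and randomized in a 1:1:1 ratio to one of the three groups". No section gives a formula for the loss allowance or a different loss rate for planning.

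**The concern.** The requirement is stated first and the loss allowance is applied to it afterwards, so 109 is naturally read as the number of women per group who must have a 6-month outcome. An enrolment target that allows for 15% loss should leave at least 109 after that loss. The target of 125 does not, so 80% power, 15% loss and 375 women cannot all hold for aim 2.

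What is at stake is the accuracy of a figure that people will rely on. A team tracking retention against 15% would believe aim 2 still had its planned size when it had fallen slightly below it. A reader checking the reported sample size could find the mismatch with one multiplication.

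**Working it through.** **Inputs** (Sample Size section): continuation rate 0.27, taken as equal in the two groups compared; margin 0.15 absolute; one-sided type 1 error 0.05 (z = 1.645); power 0.80 (z = 0.842); loss 0.15; 125 enrolled per group. Allocation is 1:1:1 (Recruitment section).

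**Step 1: reproduce the protocol's 109.** Non-inferiority of two proportions, unpooled normal approximation, true difference zero:

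n = (1.645 + 0.842)² × 2 × 0.27 × 0.73 / 0.15² = 108.3, rounded up to 109 per group.

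This matches exactly. The formula has no term for loss, so 109 is a number of women with outcome data.

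**Step 2: apply the stated loss to the stated enrolment.**

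- Per group: 125 × 0.85 = 106.25, against 109. Shortfall 2.75.
- Overall: 3 × 106.25 = 318.75, against 327. Shortfall 8.25.

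**Step 3: see how 125 could have arisen.**

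- Multiplying by 1 + loss: 109 × 1.15 = 125.35, rounded to 125; × 3 = 375. This agrees with the protocol.
- Dividing by 1 − loss: 109 / 0.85 = 128.2, rounded up to 129; × 3 = 387. Check: 129 × 0.85 = 109.65, while 128 × 0.85 = 108.8 falls just short.

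Multiplication is the likely route, but the shortfall in step 2 does not depend on how 125 was obtained.

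**Step 4: power for aim 2.** Power = Φ(0.15 / √(2 × 0.27 × 0.73 / n) − 1.645).

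| Loss from 125 | Evaluable per group | Power |
|---|---|---|
| 10% | 112.5 | 81.3% |
| 12.8% | 109 | 80.2% |
| 15% | 106.25 (106) | 79.3% (79.2%) |
| 20% | 100 | 77.2% |

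**Step 5: the loss that 125 per group can absorb.**

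- To keep 109 evaluable: 1 − 109/125 = 12.8%.
- To keep exactly 80% power (108.3 evaluable): 1 − 108.3/125 = 13.3% (rounded down from 13.36%).

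**Step 6: aim 1.** Power = Φ(8 / √(2 × 18² / n) − 1.645). With n = 63 this gives 80.2%, consistent with the protocol's 63. With n = 106 it gives 94.4%. Aim 1 is not affected.

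**The case against.** The strongest objection is that the discrepancy is too small to matter.

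- **Size.** Power falls by about one point from its value at 109 and is under one point short of 80%. That is less than the uncertainty in the inputs. With 106 per group and a continuation rate of 26% in place of 27%, the same formula gives Φ(0.15 / √(2 × 0.26 × 0.74 / 106) − 1.645) = 80.1%. This stands as a comment on importance. It does not make the plan's own figures agree.
- **Retention may be better than planned.** The Patient Incentives item says of the payments: "This dollar amount is in line with other projects that have had >90% retention over one year in our Bronx population". At 10% loss aim 2 would have about 81% power. But the protocol chose 15% for planning, and the sentence fails at that rate. The section on recruitment, follow-up and retention also describes a population with historically high attrition, so loss could exceed 15%.
- **Some lost women may still have a known outcome.** Participants are asked to tell the coordinators when they stop breastfeeding. A woman who reports stopping and is then lost might be counted as not continuing at 6 months. Of the 18.75 women lost per group, only 2.75 (about 15%) would need to be classified this way to restore 109. So 106 is a complete-case figure. However, the Analysis Plan does not say such women would be counted, resumption is possible, and recovering only those who stopped could bias the comparison.
- **The wording.** The protocol attaches 80% power to 109 per group and never separately states the power of 375 women at 15% loss. It also speaks of needing to enrol 109, which might suggest that loss is already included. Step 1 of the working rules out the second reading, because 109 is the result with no loss term. On the first, a loss allowance added directly after the requirement can only be meant to preserve it.

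**Conclusion.** The inconsistency is real and minor. At the protocol's own 15% loss, 125 women per group leave 106.25 evaluable against a stated need of 109, and aim 2 has 79.2–79.3% power against the stated 80%. The enrolment target supports the 109 only up to 12.8% loss.

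These figures assume a 27% continuation rate in both groups compared, a true difference of zero, the normal approximation that reproduces the protocol's 109, equal loss in the groups, and analysis only of women with 6-month data. Aim 1 keeps about 94% power with 106 per group. Nothing here shows the trial to be materially underpowered; a sample size statement is wrong as written.

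**What to change.** Keep 375 and replace the loss-to-follow-up sentence in the Sample Size section with wording such as:

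> 375 women (125 per group) give 109 evaluable per group at up to 12.8% loss; at 15% loss (about 106 per group) power for the 15-point margin is about 79%.

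The cost is one sentence. It needs no additional women and no design change, and the 375 in the Frequency section stays as it is. The only consequence is that the power implied at 15% loss becomes slightly less favourable.

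If the team would rather keep 109 evaluable at 15% loss, the consistent target is 129 per group, 387 in total, which is 12 more women. The size of the shortfall does not call for that.
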